6.2.6. Cost of equipment per patient

Equipment	Unit Cost
Omron M4 BP Monitor	37.93
Omron HEM-9210 BP Monitor	130.00
Glucomen Areo Glucometer	2.00
Glucomen Areo Glucometer Strips	5.95
Glucomen Areo Glucometer Lancets	3.77
Sharps Bin	3.00
Belter CF-989 Weigh Scale	20.00

6.3. Secondary Analysis Variables

6.3.1. Safety of Fresh Start

Safety is to be determined by the following as entered in study dataset over the 12-week assessment period:

- Number of deaths
- Number of emergency department admissions
- Number of hospital admissions

6.3.2. Impact of Fresh Start on clinical outcomes.

To evaluate the impact of Fresh Start on clinical outcomes the following outcomes will be assessed:

- HbA1c, recorded via patient records at baseline, upon completion of 12-week assessment period and at 6 months
- Lipids, incl. LDL and non-HDL cholesterol, recorded via patient records at baseline, upon completion of 12-week assessment period and at 6 months
- Weight, recorded via patient records at baseline, upon completion of 12-week assessment period and at 6 months
- Diabetes Distress Scale score (DDS), as recorded within HUMA once monthly across the 12-week assessment period and also at 6 months
- Blood glucose time-in-range, as recorded within HUMA over the 12-week assessment period

Time-in-range is to be defined as the percentage of time that a participant spends with their blood glucose levels between 70 to 180 mg/dl.

- Systolic blood pressure (SBP), as recorded within HUMA, as recorded within HUMA over the 12-week assessment period

7. Statistical Methodology

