Clinical protocols. A series of best-practice CRG approved clinical protocols are in place to be triggered based on thresholds and values captured via the Huma app and as part of the VGC sessions. Protocol examples include medications review, foot care, renal, and mental health.

Digital remote patient monitoring using blood pressure and blood sugar devices in combination with a smartphone application ('the Huma app'). Participants are provided with home monitoring devices and download the Huma app. Participants are shown how to use the devices, how to input measurements into a smart phone and how to set personal goals. Data recorded via the Huma app is self-reported and includes activity data, diet information, blood glucose measurements, blood pressure measurements, weight, and the Diabetes Distress Scale (a self-reported questionnaire used to measure distress related to living with diabetes). A Health Care Assistant (HCA) observes these data via a Huma clinician dashboard that complements the Huma app. The HCA presents these data in combination with relevant EPR data to the PN for review ahead of each VGC appointment.

One-to-one routine patient review. At the end of the 12-weeks participants are invited to a one-to-one review session with their primary care practice. The patient's progress over the 12-week service is reviewed and a decision is made whether to discharge patient, repeat them for another 12 weeks on Fresh Start, or escalate them to MDT.

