5.2.2. Matched Control Group

Several of the study's objectives and associated outcome measures will require a control group for comparison. This includes the primary objective investigating cost-effectiveness and secondary objectives investigating safety and efficacy of Fresh Start on clinical outcomes.

To achieve this, the study will establish a matched control group using propensity score matching (PSM). PSM uses statistical techniques to construct an artificial control group by matching each study participant with a non-treated participant of similar characteristics. This is achieved by estimating the probability that a person would enrol in a program given a set of pre-defined characteristics, with the resulting probability providing a 'propensity score'.

Data for the matched control group will be identified using NWL's Whole of Systems Integrated Care (WSIC) database. WSIC links provider data from four acute, two mental health and two community Trusts across eight CCGs, social care data from eight boroughs and 380 GP practices to generate an integrated care record.

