6.1. Summary of Analysis Variables

Primary Objective	Outcome	Source	Freq.	Comp. w/ control?
1) To assess the feasibility of uptake amongst people with 'high risk' or 'very high risk' type 2 diabetes .	Patients offered Fresh Start vs. enrolled	EPR	Once	No
	Patients enrolled vs. downloading Huma app	Huma	Once	No
2) To assess the usability of Fresh Start amongst people with 'high risk' or 'very high risk' type 2 diabetes .	Number of VGCS attended	EPR	Every 4 weeks	No
	Number of Fresh Start emails opened	KD	Twice weekly	No
	Number of blood glucose measurements recorded	Huma	Daily	No
	Number of blood pressure measurements recorded	Huma	Daily	No
	Number of weight* measurements recorded	Huma	Daily	No
	Number of Diabetes Distress Scale measurements recorded	Huma	Monthly	No
3) To assess the acceptability of Fresh Start amongst people with 'high risk' or 'very high risk' type 2 diabetes .	Interviews with patients (x10)	Interview	At 12 weeks	No
4) To assess the acceptability of Fresh Start amongst HCPs .	Interviews with healthcare professionals (HCPs, x10)	Interview	After intervention	No
5) To assess the cost-effectiveness of delivering Fresh Start.	Number of primary care appointments per patient	EPR	Data extracted from EPR	Yes
	Cost per appointment per patient	EPR	Data extracted from EPR	Yes
	Cost of equipment per patient	Huma	N/A	No

* In the event where BMI data is more routinely collected the endpoint may be adjusted to BMI

Secondary Objective	Outcome	Source	Freq.	Compare with control?
1) To assess the safety of Fresh Start.	Number of deaths	EPR	Data extracted from EPR	Yes
	Number of emergency department admissions	WSIC	Data extracted from WSIC	Yes
	Number of hospital admissions	WSIC	Data extracted from WSIC	Yes
2) To assess the impact of Fresh Start on clinical outcomes .	HbA1c	EPR	Baseline, 12 weeks, 6 months	Yes
	Lipids, incl. LDL and non-HDL cholesterol	EPR	Baseline, 12 weeks, 6 months	Yes
	Weight *	EPR	Baseline, 12 weeks, 6 months	Yes
	Diabetes Distress Scale score (DDS[iii])	Huma	Monthly during service (and at 6 month follow-up appt.)	No
	Blood glucose time-in-range	Huma	Daily	Yes
	Systolic blood pressure (SBP)	Huma	Daily	Yes

* Note, if patient Height is also recorded BMI may be presented as an alternative

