	Lipids, incl. LDL and non-HDL cholesterol	Yes	Summary stats of Lipids by visit (BL, W12, M6) Comparison within & between groups via mixed model (if available)
	Weight (or BMI as appropriate)	Yes	Summary stats of Weight by visit (BL, W12, M6) Comparison within & between groups via mixed model
	Diabetes Distress Scale score (DDS[iii])	No	Summary stats of DDS at per visit (M0, M1, M2, M3). Comparison within groups via mixed model (if available)
	Blood glucose time-in-range	Yes	Summary stats of days in range up to 6 months post enrollment

Imperial Clinical Trials Unit	SUB-STUDY SAP TEMPLATE – SUB-ANALYSES AND OBSERVATIONAL STUDIES	SOP_TEM_BS002
-------------------------------	---	---------------

Secondary Objective	Outcome	Comp. w/ control?	Analysis Methods
			Comparison against control via mixed model (if available)
	Systolic blood pressure (SBP)	Yes	Summary stats of SBP Comparison between groups via mixed model (if available)

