Within-group change from first DDS score to last DDS score will be assessed via a mixed-effects model taking DDS Score as dependant variable and adjusting for covariates; study day (of reading), sex, age, social deprivation index and allowing for clustering by GP Practice

- **Blood glucose time-in-range, as recorded within HUMA over the 12-week assessment period**

Investigating difference between means of days in-range after 12-weeks will be analysed using mixed-effects model adjusting for covariates; sex, age, social deprivation index and allowing for clustering by GP Practice.

The above analysis is dependent on a suitable number of data points being collected per patient to assess time-in-range. If this analysis is deemed not feasible. Change in blood glucose will be presented using the same method as for HbA1c, Lipids & Weight. First blood glucose reading will be taken as baseline per patient.

Summary statistics displaying mean, SD, median, minimum & maximum blood glucose will be produced at for first reading and last reading.

- **Systolic blood pressure (SBP), as recorded within HUMA, as recorded within HUMA over the 12-week assessment period**

Summary statistics displaying mean, SD, median, minimum & maximum blood glucose will be produced at for first reading and last reading.

Investigating difference between means of SBP after 12-weeks will be analysed using mixed-effects model adjusting for covariates; sex, age, social deprivation index and allowing for clustering by GP Practice

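### SBP and blood glucose time-in-range are marked for comparison with controls, but both are taken from the Huma app and no control variable is named to stand in for either

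*SAP*

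**What the plan says.** Protocol 3.6 and SAP 6.1 list SBP and time-in-range with source Huma, daily frequency and control comparison 'Yes'. SAP 6.3.2 defines them as "Systolic blood pressure (SBP), as recorded within HUMA, as recorded within HUMA over the 12-week assessment period" and "Blood glucose time-in-range, as recorded within HUMA over the 12-week assessment period".

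The app and devices belong to the service: "Participants are provided with home monitoring devices and download the Huma app" (SAP 5.2.1). Controls are formed by "matching each study participant with a non-treated participant of similar characteristics" (SAP 5.2.2), with WSIC as the data source for the control group as a whole.

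For analysis, SAP 7.2 has "Comparison against control via mixed model (if available" for time-in-range and "Comparison between groups via mixed model (if available" for SBP, both ending in an availability proviso. SAP 7.6.2 drops the proviso. For SBP it reads "Investigating difference between means of SBP after 12-weeks will be analysed using mixed-effects model adjusting for covariates; sex, age, social deprivation index", plus clustering by practice. For time-in-range, its only condition is enough data points per patient. Failing that, change in blood glucose is analysed as for HbA1c, lipids and weight, with each patient's first reading as baseline. The SAP revision table (version 0.2) records that the time-in-range benchmark was removed and will be added post hoc.

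**The concern.** A between-group analysis needs the outcome in both groups. Here the stated source belongs to the intervention. As written, the analysis either cannot be run (time-in-range) or needs someone to choose a control variable that the plan does not name (SBP). If that choice is made after extraction, it is made with the data in view. A reported SBP difference could then reflect where and how the pressure was taken rather than Fresh Start. Protocol 3.11 calls these comparisons exploratory but still has differences reported with 95% CIs, so the estimates would be published and read.

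**Working it through.** **1. Source against control flag** (protocol 3.6; SAP 6.1)

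| Clinical outcome | Source | Compare with control | Can the source type exist for controls? |
|---|---|---|---|
| HbA1c | EPR | Yes | Yes |
| Lipids | EPR | Yes | Yes |
| Weight | EPR | Yes | Yes |
| Diabetes Distress Scale (DDS) | Huma | No | Not needed |
| Time-in-range | Huma | Yes | None described |
| SBP | Huma | Yes | None described |

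Four rows are coherent. The last two alone combine a Huma source with a 'Yes'.

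**2. Does another section supply a control variable?**

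- SAP 5.2.2 and 7.1.2 name WSIC for the control group but no SBP or glucose field.
- The SAP 7.2 proviso does not say what would qualify. The same words are attached to lipids, which come from the EPR, and to DDS, which has no control comparison, so they do not identify control data.
- The SAP 7.6.2 data-point condition concerns the number of readings per patient, not their source. The glucose fallback points to methods that include a between-group model, again with no control source.
- Protocol 3.9 lists blood pressure and blood glucose at the month-6 practice appointment, and protocol 3.7 has staff copy the latest Huma values into the EPR before each video group consultation (VGC). Both concern Fresh Start participants only.

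**3. What the SBP model would estimate.** SAP 7.6.2 lists sex, age and deprivation for SBP. It lists no treatment term and no baseline SBP, whereas the HbA1c, lipids and weight model has both. SBP is not a matching variable in SAP 7.1.2 either. Suppose a treatment term is added, Fresh Start contributes home readings and controls contribute practice readings. With d the mean home-minus-practice offset:

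expected difference = treatment effect + any baseline imbalance + d.

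The offset enters one for one, in either direction. A practice-recorded baseline term would address the imbalance but leave d, because d sits in the follow-up values of one group only.

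**4. Scale.** The documents give neither d nor an SD for SBP. Take 300 per group (the planned minimum, matched 1:1) and an assumed SD of 15 or 20 mmHg, with no clustering and no baseline adjustment:

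half-width = 1.96 × SD × √(2/300)

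- SD 15: 1.96 × 15 × 0.0816 = 2.4 mmHg
- SD 20: 1.96 × 20 × 0.0816 = 3.2 mmHg

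An offset of about 2.4 to 3.2 mmHg would thus equal the sampling half-width. This is a yardstick, not evidence that such an offset exists.

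**5. Table list** (SAP Appendix 1). A between-group table is listed for time-in-range and for DDS, although DDS is marked 'No'. No SBP table is listed at all.

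**The case against.** The strongest reply is that the plan is less committed, and less empty, than it looks. WSIC is named for controls and links 380 GP practices. Eligibility uses SBP above 140 mm Hg and the EPR searches are built on the eligibility criteria, so practice SBP is an evident candidate. SAP 7.2 makes both comparisons conditional, and the revision table openly says that the time-in-range benchmark is unsettled. The outcomes are exploratory.

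Most of this stands, and it limits the point. A reader might infer that no control source is named at all, or that an SBP comparison is impossible. The documents do not support either: the gap for SBP is an unstated variable. A reader might also infer that the sponsor plans to set home readings against practice readings. Nothing says so; it is one way the gap could be filled.

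Nor should copying of Huma values into the EPR be read as fatal to an EPR-based comparison. The VGCs fall at about weeks 1, 5 and 9 (first about one week after onboarding, then 1 + 4 and 5 + 4), so suitable follow-up windows could exclude copied values by date, except where a patient repeats the service.

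What does not stand is that the proviso or the disclosed benchmark closes the gap. Neither says which control data would be used.

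**Conclusion.** The point holds as a mismatch between source and control flag for two exploratory outcomes, and it is minor. Time-in-range, and the Huma glucose fallback, have no control data in the stated source, and the benchmark is left to be set post hoc. An SBP comparison may be feasible from GP records, but it needs a named variable, the same source in both groups, and a model with treatment and baseline terms. The size of any SBP distortion is unknown: it equals whatever setting offset exists, and the 2.4 to 3.2 mmHg yardstick rests on assumed SDs and ignores clustering. A reader might extend this to the feasibility, cost or safety results. It does not reach them, because none uses these two variables as a between-group outcome.

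**What to change.** **Time-in-range and the glucose fallback.** Set control comparison to 'No', report within Fresh Start only, and remove the between-group time-in-range table. Drop the post-hoc benchmark or fix it before analysis. As a separate tidy-up, remove the between-group DDS table.

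**SBP: decide before control data are extracted.**

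- *Either* set it to 'No' and report Huma SBP within Fresh Start.
- *Or* define the between-group outcome as practice-recorded SBP from EPR/WSIC in both groups, in the same pre-stated windows, with treatment and baseline SBP terms. Close the baseline window before onboarding, since first app readings are entered at that appointment. Set follow-up windows or rules that exclude Huma values copied into the EPR before each VGC, including for patients who repeat the service. Revert to 'No' if those values cannot be excluded or if coverage falls below a pre-stated minimum.

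Add an SBP table to match the choice.

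**Cost.** The first part and the 'No' choice for SBP are wording edits to protocol 3.6, SAP 6.1, 7.2 and 7.6.2 and the table list. The practice-recorded choice needs an extraction of routine SBP and a coverage check. It will yield fewer readings: blood pressure is not among the practice measurements listed at baseline or 12 weeks in protocol 3.7 (HbA1c, lipids, weight) and is listed only at month 6 in protocol 3.9. The documents do not show that copied values are flagged in the EPR, so the exclusion rule should be tested before it is relied on.

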7.1. General Methodology

7.1.1. Descriptive Output for Feasibility Outcomes

To investigate feasibility of Fresh-Start, analysis of primary endpoints will be descriptive in nature to establish how many patients engaged with the Fresh Start program, and if so, to what extent.

Continuous variables will be presented as means and standard deviations if normally distributed, and as medians and inter-quartile ranges for skewed data. Categorical variables will be presented as frequencies and percentages.

Details of the output provided will be included within sections 7.5.1 – 7.5.5. Dummy shells for tables, figures and listings will be provided within appendix 2.

7.1.2. Propensity Score Matching

For the primary cost-benefit comparison and secondary safety and efficacy comparisons, study data will be compared against a matched-control group established via propensity score matching. This is achieved by deriving a propensity score for each enrolled patient based on the following characteristics:

- Age
- Gender
- Geographical proximity
- Social deprivation index (by practice)

- Ethnicity

Using the above categories, taking 'arm' as the dependent variable, logistic regression using a generalised logit model will be used to generate the estimated propensity scores. Scores are also applied to a control 'arm' taken from the WSIC database as section 5.2.2 with everyone in the matched control identified within one month of the index case. The scores are then used to 'pair-up' patients within both groups, patients will be matched on a 1:1 basis without replacement.

Scores are to be calculated using PSOCORE in STATA. Matching is to be carried out using PSMATCH2 (or a suitable alternative). Balancing on matching variables is to be checked once matching is completed using PSTEST. If any variable is found to be unbalanced the matching is repeated, either adjusting the matching method or caliper used.

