3.5 Matched control group

A number of the study's objectives and associated outcome measures will require a control group for comparison. These objectives include:

- To assess the cost-effectiveness of delivering Fresh Start;
- To assess the safety of Fresh Start; and
- To assess the impact of Fresh Start on clinical outcomes.

This study will create a matched control group using propensity score matching (PSM),⁹ a quasi-experimental method used to mimic the characteristics of a randomised control trial that has been shown to reduce biases.¹⁰ PSM uses statistical techniques to construct an artificial control group by matching each study participant with a non-treated participant of similar characteristics. PSM computes the probability that a person would enrol in a program based on pre-defined characteristics, giving a 'propensity score'.

The propensity score for the study will be based on the following characteristics:

- Age
- Gender
- Risk category (see inclusion criteria)
- Geographical proximity
- Social deprivation index (by practice)

Each individual in the matched control group will be identified within one month of the index case.

Imperial College London

The matched control group will be identified using NWL's Whole of Systems Integrated Care (WSIC) database. WSIC links provider data from four acute, two mental health and two community Trusts across eight CCGs, social care data from eight boroughs and 380 GP practices to generate an integrated care record.

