3.11 Data analysis

The research team will not have access to any personal or identifiable patient data as part of the project. Data will be de-identified before being transferred to WSIC's de-identified data (DID) environment and made available to approved researchers. Any data extracted from the secure environment after analysis by the research team will be at an aggregate level only.

All outcomes will be reported using descriptive statistics with tables and graphical presentations of findings. Continuous variables will be presented as means and standard deviations if normally distributed, and as medians and inter-quartile ranges for skewed data, whilst categorical variables will be presented as frequencies and percentages.

To assess the pre-test/post-test change on clinical outcomes the appropriate generalized mixed model approach will be used to account for repeated measurements and clustering of GP practices and including important covariates in the model.

To create a matched control group from NWL's WSIC database, a 1:1 propensity score matching (PSM) analysis will be performed using age, gender, risk category, geographical proximity and social deprivation index as matching variables. R statistical software will be used for estimating PS by logistic regression and for balance and sensitivity checks.

Comparisons with the control group for clinical outcomes will be exploratory and differences with 95% CI will be reported using the appropriate generalized mixed model.

Interviews conducted with participants and healthcare professionals will be analysed using NVivo, where responses will undergo thematic analysis using an inductive approach to derive key themes.

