4.3 Inclusion criteria

- Patients over the age of 18 with the capacity to give consent
- Patients with 'high risk' OR 'very high risk' T2DM as defined by:
- **Very high risk - T2DM with existing ASCVD OR T2DM without ASCVD but with any 3 of the following:**
 - HbA1c >58 mmol/mol
 - SBP >140 mm Hg
 - Non-HDL >3.35 mmol/L or LDL-C >2.5 mmol/L
 - Nephropathy (eGFR <45 ml/min, or Urine ACR >3 mg/mol)
 - Retinopathy
 - Neuropathy (including moderate/high risk feet, previous foot ulceration and erectile dysfunction)
 - Currently smoking
- **High risk - T2DM without ASCVD but with any 2 of the following:**
 - HbA1c > 58 mmol/mol
 - SBP >140 mm Hg
 - Non-HDL >3.35 mmol/L or LDL-C >2.5 mmol/L
 - Nephropathy: eGFR <45 ml/min or Urine ACR >3 mg/mol
 - Retinopathy

- Neuropathy (including moderate/high risk feet, previous foot ulceration and erectile dysfunction)
- Currently smoking
- Black, Asian and minority ethic (BAME) status

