5.3. Study Population

The study population includes people with 'high risk' and 'very high risk' type 2 diabetes as defined by guidance for primary care from NHS England and NHS Improvement (London). All additional inclusion and exclusion criteria are defined within section 5.4 below:

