5.5. Sample Size

The study will seek to collect and analyse data from a minimum of 300 participants to Fresh Start. With an estimated enrolment rate of 20%, 1,500 eligible patients will need to be identified and we will be able to estimate this rate within a 95% confidence interval of +/-3%, accounting for variance inflation due to clustering with the assumption of 10 GP practices and Intraclass Correlation Coefficient (ICC) of 0.05.

The study's secondary objectives are exploratory only and will not be demonstrated to a level of statistical significance in this study.

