6.2.5. Cost-effectiveness of delivering Fresh Start

Cost-effectiveness is to be determined by the following measures:

- Number of primary care appointments per patient - as entered in study dataset over the 12-week assessment period
- Cost per appointment per patient - as entered in study dataset
- Cost of equipment per patient – defined below:

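### The SAP drops the protocol's risk category from the propensity score without a reason, leaving the primary appointment and cost comparison open to confounding by risk mix

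*SAP*

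**What the plan says.** **Protocol.** Section 3.5 lists risk category among the characteristics that make up the propensity score. Section 3.11 repeats it: "a 1:1 propensity score matching (PSM) analysis will be performed using age, gender, risk category, geographical proximity and social deprivation index".

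**SAP.** Section 7.1.2 says "This is achieved by deriving a propensity score for each enrolled patient based on the following characteristics" and then lists age, gender, geographical proximity, practice-level deprivation and ethnicity. Risk category is absent and ethnicity is new. The same section makes this score the basis of the primary cost comparison and of the secondary safety and efficacy comparisons. Matching is 1:1 without replacement.

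**Control pool.** SAP 5.2.2 says "Data for the matched control group will be identified using NWL's Whole of Systems Integrated Care (WSIC) database". Neither that section nor 7.1.2 says that a WSIC control must be high or very high risk. SAP 5.3 says "The study population includes people with 'high risk' and 'very high risk' type 2 diabetes as defined by guidance for primary care", so the restriction is probably intended, but it is not written for controls.

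**Reason for the change.** None is stated. The SAP revision log mentions only the time-in-range benchmark. That is weak evidence, because the log covers changes between SAP versions and not departures from the protocol.

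**The concern.** Risk category is the only variable in the protocol's score that measures disease severity, and the SAP removes it. If very-high-risk patients are more or less likely to enrol, and also use primary care more, the matched groups will differ in expected appointments before Fresh Start has any effect. The comparison concerned serves a primary objective.

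Ethnicity is not a substitute. In Protocol 4.3, "Black, Asian and minority ethic (BAME) status" is listed under high risk and is not among the very-high-risk criteria. It says nothing about the eight clinical criteria: ASCVD, HbA1c, SBP, non-HDL/LDL, nephropathy, retinopathy, neuropathy and smoking.

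The exploratory safety composite in SAP 7.6.1 has the same gap, with no covariates stated. HbA1c, lipids and weight are less exposed because their models adjust for the baseline value.

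**Working it through.** **Step 1. Does anything later in the SAP recover risk category?**

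| Step | Variables covered | Risk category? |
|---|---|---|
| Balance check, PSTEST (7.1.2) | Matching variables only | No |
| Demographics table (7.4) | Age, gender, ethnicity, deprivation, location | No |
| Appointment model (7.5.5) | Sex, age, deprivation, practice clustering | No |
| Cost-per-appointment model (7.5.5) | Same | No |
| Replacement of controls with missing data (8) | Fit to the matching algorithm, preserved balance | No |
| Baseline clinical tables (7.6.2) | HbA1c and lipids | 2 of the 8 clinical criteria |

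SBP does not reliably add a third. It is sourced from the Huma app, its between-group comparison is planned only if data are available, its summary text in 7.6.2 refers to blood glucose, and Appendix 1 lists no SBP table.

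Restricting controls to eligible patients would remove low-risk controls. It would not balance high against very high risk.

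**Step 2. Size of the bias if there is no true effect.** Neither document gives a figure to reproduce or the inputs needed, so every input here is assumed. Let p_C be the very-high-risk share in controls, OR the effect of that status on the odds of enrolment, and R the appointment rate ratio, very high v high risk.

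- o = p_C / (1 − p_C)
- p_FS = OR·o / (1 + OR·o)
- Spurious rate ratio = (p_FS·R + 1 − p_FS) / (p_C·R + 1 − p_C)

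Example: p_C = 0.5, OR = 2, R = 1.5. Then p_FS = 2/3 = 0.667, the gap is 16.7 points, and the ratio is 1.333/1.25 = 1.067.

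| p_C | OR | p_FS | Gap (points) | R = 1.25 | R = 1.5 |
|---|---|---|---|---|---|
| 0.3 | 2 | 0.462 | +16.2 | 1.038 | 1.070 |
| 0.5 | 2 | 0.667 | +16.7 | 1.037 | 1.067 |
| 0.7 | 2 | 0.824 | +12.4 | 1.026 | 1.046 |
| 0.3 | 0.5 | 0.176 | −12.4 | 0.971 | 0.946 |
| 0.5 | 0.5 | 0.333 | −16.7 | 0.963 | 0.933 |
| 0.7 | 0.5 | 0.538 | −16.2 | 0.966 | 0.940 |

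With OR = 1 the ratio is 1.000. The range is therefore 0.93 to 1.07.

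**Step 3. Does matching on the other variables remove it?** Simulation, all inputs assumed:

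- 10 practices with 150 eligible patients each, 20% enrolled.
- A control pool of 30 other practices with 150 eligible each (4,500).
- About half very high risk, correlated with age.
- Score on age, sex, ethnicity and deprivation; location left out.
- 1:1 matching without replacement, caliper 0.2 SD of the logit.
- Poisson regression on arm, age, sex and deprivation.
- 300 runs per setting, Monte Carlo error about ±1%.

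| OR | Omitted, R = 1.25 | Omitted, R = 1.5 |
|---|---|---|
| 0.5 | 0.978 | 0.944 |
| 1 | 1.004 | 0.997 |
| 2 | 1.024 | 1.054 |

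With OR 0.5 or 2, the risk-mix gap after matching was 12.6 to 13.2 points. With risk category restored, the gap was at most 0.2 points and the ratio 0.991 to 1.004. About 99% of enrolled patients were matched either way. A second simulation with a different set-up (R = 1.5, log-odds of enrolment shifted by 0.4 or 0.8 in either direction) gave 0.93 to 1.09 omitted and 0.99 to 1.00 restored.

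**Step 4. Compare with precision.** CI factor = exp(1.96·√(k·DE·2/(300·m))), where m is mean appointments and k is variance/mean. SAP 5.5 describes its sample size as "accounting for variance inflation due to clustering with the assumption of 10 GP practices and Intraclass Correlation Coefficient (ICC) of 0.05". Borrowing that ICC for appointments, with 300/10 = 30 per practice, gives DE = 1 + 29 × 0.05 = 2.45.

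| m | k = 1 | k = 2 |
|---|---|---|
| 5 | 1.119 | 1.172 |
| 2.5 | 1.172 | 1.251 |

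Two means are shown because the SAP states two windows. Section 6.2.5 has "Number of primary care appointments per patient - as entered in study dataset over the 12-week assessment period", while the table in 7.2 runs to 6 months. With no design effect, m = 5 and k = 1, the factor is exp(1.96·√(2/1500)) = 1.074.

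**The case against.** The strongest opposing case has five parts.

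- **The population is already high risk, and the study is a feasibility study whose primary analyses are mainly descriptive.** This limits the weight of the point. It does not remove it: SAP 7.2 and 7.5.5 specify between-group models for this primary objective, and the high v very-high split stays unmatched even in an eligible pool.
- **Adding ethnicity as risk category left may have been deliberate.** Possibly, and the revision log cannot settle it. A deliberate change still needs a stated reason and a matching protocol amendment.
- **The restored simulation returns about 1.00 by construction**, because risk category was the only omitted confounder built in. This stands. It shows that the fix removes this bias, not that the comparison would become unbiased. Prior appointment use and willingness to join are not matched on in either document.
- **The bias is small against the CI, and the design effect is borrowed.** The enrolment ICC need not apply to appointments, and 30 per practice need not hold for controls drawn from WSIC's 380 practices. Without any design effect the factor is 1.074 against a bias of up to 1.070, so the bias is still inside, though barely. A CI does not allow for systematic bias in any case, and more patients would not remove it.
- **No size is given for cost.** This stands. The figures concern appointment counts and do not carry over directly to cost per appointment.

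**Conclusion.** The concern holds. Two sections of the protocol put risk category in the score, the SAP leaves it out without explanation, and none of the SAP's later checks or appointment and cost models recovers it. That rests on the text alone and is firm.

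The size of the bias is illustrative: a spurious appointment rate ratio of 0.93 to 1.07 under the assumed inputs, or 0.944 to 1.054 after matching on the other simulated variables. It needs risk category to affect both enrolment and appointment use, and without an effect on enrolment there is none. Direction cannot be known from the documents. Under the assumptions shown, the bias lies inside the 95% CI. This should be fixed before the matched comparison is run; it does not affect the uptake and usability results, which use no control group.

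**What to change.** 1. Restore risk category to the score in SAP 7.1.2 and keep ethnicity.
2. Show risk category by group in the PSTEST output and in table 2.1.
3. State that WSIC controls must meet the Protocol 4.3 and 4.4 criteria that can be coded there, and apply the same rule to replacement controls.
4. If the omission was deliberate, record the reason, amend the protocol, and adjust for risk category in the appointment and cost models. If the reason is that some criteria cannot be coded in WSIC, that adjustment would meet the same obstacle. In that case name the missing components, use those available, and report the remainder as a limitation.

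**Cost.** SAP wording and one matching variable the protocol already plans, assuming WSIC holds the data. Matches may be slightly fewer or looser. In the simulation almost none were lost, with an assumed pool of 4,500 eligible controls.
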